4.3.2. Prior and Concomitant Procedures

The procedures are coded using Medical Dictionary for Regulatory Activities (MedDRA) of the version at database lock. The prior and concomitant procedures are defined similarly as the prior and concomitant medications. The summary of prior and concomitant procedures will be

presented with number (%) by SOC and PT. Each subject will be counted only once for each preferred term within a SOC. Similarly, for determination of MedDRA SOC incidences, subjects who experience multiple procedures under the same SOC will be counted only once for that SOC.

4.4. Protocol Deviations

A protocol deviation is defined as a change, divergence, or departure from the approved study design or procedures defined in the protocol. Important protocol deviations are a subset of protocol deviations that may significantly impact the completeness, accuracy, and/or reliability of study data or that may affect the subject's rights, safety, or well-being.

Current ICH GCP guidelines request that the important protocol deviations must be listed in the clinical study report. These may include, but are not limited to:

- Subjects that are dosed on the study despite not satisfying the inclusion criteria.
- Subjects that develop withdrawal criteria whilst on the study but are not withdrawn.
- Subjects that receive the wrong treatment or an incorrect dose.

A summary table will be provided as the number (%) of subjects with at least one important protocol deviation and the number (%) of subjects in each category by study periods. Protocol deviations will be summarized in DB and OLE periods.

4.5. Treatment Exposure and Compliance

Descriptive statistics will be provided for the following.

- Duration of treatment in DB period in weeks:
 - For subjects who have NOT been enrolled in OLE period: $[\min(\text{DB last dose date} + 27, \text{DB period end date}) - \text{DB first dose date} + 1]/7$
 - For subjects who have been enrolled in OLE Period: $[\text{OLE first dosedate} - \text{DB first dose date}]/7$.
- Duration of treatment in OLE period in weeks:
 - $[\min(\text{OLE last dose date} + 13, \text{OLE period end date}) - \text{OLE first dosedate} + 1]/7$.
- Duration of treatment over study in weeks:
 - For subjects who have NOT been enrolled in OLE period: $[\min(\text{last DB last dose date} + 27, \text{DB period end date}) - \text{DB first dose date} + 1]/7$
 - For subjects who have been enrolled in OLE Period: $[\min(\text{OLE last dose date} + 13, \text{OLE period end date}) - \text{DB first dose date} + 1]/7$.
- Number of doses received per subject will be summarized as 1 dose, 2 doses, 3 doses, 4 doses for DB period, and up to 17 doses for OLE period.
- Treatment compliance is defined as the number of administrations that the subject is compliant divided by the total number of administrations that the subject is planned to take from the first administration of study medications up to the actual last

administration of study medications. Note that a given administration will be considered noncompliant if the subject does not take the planned dose as required by the protocol. No imputation will be made for subjects with missing or incomplete data. Note that the treatment compliance may be summarized in DB and OLE periods separately.

All study drug exposure data will be listed including reasons for dose not administered.

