#### **4.4 Study Treatment**

For Phase 2b, subjects will be randomized to receive KPL-716 or matching placebo on Day 1 and will remain in the same treatment arm throughout the Double-Blind Period, then all subjects will have the option to participate in the OLE Period, starting dosing at the End of Week 16 Visit.

Phase 2b: [Figure 1](#)

- Arm A: KPL-716 at 540 mg SC on Day 1 and at Weeks 4, 8, and 12 during the Double-Blind Period
- Arm B: KPL-716 at 360 mg SC on Day 1 and at Weeks 4, 8, and 12 during the Double-Blind Period
- Arm C: KPL-716 at 120 mg (see Pharmacy Manual for formulation instructions) SC on Day 1 and at Weeks 4, 8, and 12 during the Double-Blind Period
- Arm D: Placebo SC on Day 1 and at Weeks 4, 8, and 12 during the Double-Blind Period

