#### **4.9 Subject Withdrawal and Replacement**

Subjects may withdraw from the study drug treatment or from the entire study at any time for any reason, without prejudice to their medical care. The Investigator also has the right to discontinue treatment with and withdraw subjects from the study for any of the following reasons:

- Adverse event

- Life threatening or other unacceptable toxicity
- Subject requires use of a prohibited concomitant medication or therapy
- General or specific changes in the subject's condition unacceptable for further treatment within the study parameters, in the Investigator's opinion
- Severe noncompliance
- Lost to follow-up (Subjects will be defined as lost to follow up if they have not responded to 3 phone calls and one certified letter)
- Subject withdrawal of consent
- A decision to modify or discontinue development of the drug

In case of study drug interruption or missed dosing visits, subjects will resume the schedule of activities in accordance with their study day.

In case of study drug discontinuation, subjects will continue to follow the schedule of activities for each visit minus dosing. Under these circumstances, the second set of biopsies will be performed at the earliest possible visit. Skin biopsies are optional.

If a subject withdraws from the entire study, the subject must complete the EOS Visit. In addition, if the early termination occurs prior to the last week of treatment, biopsies should be collected at the EOS visit.

If the subject withdraws from study treatment and also withdraws consent for disclosure of future information, no further evaluations should be performed, and no additional data should be collected. The Sponsor may retain and continue to use any data collected before such withdrawal or consent.

Subjects will not be replaced.

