1.2. Study Design

This is a randomized, double-blind, placebo-controlled study to investigate the efficacy, safety, tolerability, PK, and immunogenicity of KPL-716 administered SC in subjects with moderate to severe PN experiencing severe pruritus.

[figure not shown]
The Phase 2b study ([Figure 1](#)) consists of a 4-week screening period and a 16-week double-blind (DB) period, followed by a 36-week open-label-extension (OLE) period. Approximately 180

subjects with moderate to severe PN experiencing severe pruritus will be randomized (at 1:1:1:1 ratio) into one of the following 4 arms:

- Arm A: KPL-716, 540 mg, SC, every 4 weeks (Q4W)
- Arm B: KPL-716, 360 mg, SC, Q4W
- Arm C: KPL-716, 120 mg, SC, Q4W
- Arm D: Placebo, SC, Q4W

A total of 4 doses of study drug will be administered during the DB Period to measure the efficacy, safety, and PK of KPL-716.

Figure 1 Phase 2b Study Design Diagram

After the DB period, all subjects will have the option to receive KPL-716 360 mg SC, Q2W during the OLE period to evaluate the long-term safety and PK of KPL-716. For subjects who complete the DB period but choose not to participate in OLE, or who terminate earlier, an End of Study (EOS) visit will be required 4 weeks following the date of last study drug dose.

Subjects will follow the schedule below:

- Screening period (minimum 7 days and maximum 28 days)
- DB period (Day 1 [Baseline] to Week 16)
- OLE period (End of Week 16 to Week 52)

The allowable visit window from Week 2 to Week 16 is \pm 2 days and thereafter to Week 52 is \pm 3 days.

Randomization and Dosing:

Subjects will be randomized 1:1:1:1 into one of the following 4 arms: KPL-716 540 mg SC, Q4W; KPL-716 360 mg SC, Q4W; KPL-716 120 mg SC, Q4W; or placebo SC, Q4W. At the end of DB period, all subjects will have the option to enter the OLE period to receive KPL-716

360 mg SC Q2W. Stratification will be performed based on sex and years since first nodule observed (i.e., ≥ 10 years vs. < 10 years).

Efficacy Assessments:

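### SAP 4.5 ends double-blind treatment duration 27 days after the last dose only for subjects outside the OLE, so a missed Week 12 dose counts as 12 weeks for them and 16 for OLE entrants

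*SAP*

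**What the plan says.** SAP 4.5 splits double-blind treatment duration by whether the subject entered the OLE.

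- Under "For subjects who have NOT been enrolled in OLE period", the formula is "\min(\text{DB last dose date} + 27, \text{DB period end date}) - \text{DB first dose date} + 1]/7". The last dose sets the end date unless the period ended earlier.
- For the others: "For subjects who have been enrolled in OLE Period: $[\text{OLE first dosedate} - \text{DB first dose date}]/7". The last double-blind dose does not appear.

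The over-study duration for OLE entrants in the same section runs from the first double-blind dose to the earlier of last OLE dose + 13 days and the OLE end date. It does not refer to the last double-blind dose either.

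The protocol allows an incompletely dosed subject to reach the OLE. Section 4.9 states: "In case of study drug interruption or missed dosing visits, subjects will resume the schedule of activities in accordance with their study day". Section 4.4 says that "all subjects will have the option to participate in the OLE Period, starting dosing at the End of Week 16 Visit", and no minimum number of double-blind doses is given.

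SAP 4.5 also tabulates the number of double-blind doses received (1 to 4) and lists all exposure data with reasons for doses not given.

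**The concern.** Two subjects with the same dosing record get different treatment durations if one enters the OLE and the other does not. OLE entry is decided after randomization. For entrants, the double-blind figure is in effect time from first double-blind dose to first OLE dose, reported under a treatment label. Time in the double-blind period is already a separate item in the disposition table (SAP 4.1).

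At stake is how exposure by arm is described in a dose-finding study. The mean duration is overstated in any arm where final double-blind doses were missed before OLE entry. The overstatement could differ between arms if missed doses or OLE uptake differ, but the documents give no rates for either.

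**Working it through.** **Inputs.** Double-blind doses are given on Day 1 and at Weeks 4, 8 and 12 (Protocol 4.4, for example "Arm A: KPL-716 at 540 mg SC on Day 1 and at Weeks 4, 8, and 12 during the Double-Blind Period"), which are Days 1, 29, 57 and 85 in the Schedule of Activities. The first OLE dose is at the Week 16 visit, Day 113, with a window of ±2 days. The last OLE dose is at Week 48, Day 337, and the final visit is Day 365.

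**Reproducing the plan's figure.** SAP 1.2 describes "a 4-week screening period and a 16-week double-blind (DB) period". For a fully dosed subject on nominal days:
- not in OLE: (min(85 + 27, 113) - 1 + 1)/7 = 112/7 = 16.0 weeks
- OLE entrant: (113 - 1)/7 = 112/7 = 16.0 weeks

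Both rules return 16 weeks.

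**Final doses missed.** The non-OLE result is the same whether the period end is taken as Day 113 or as 28 days after the last dose.

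| Last double-blind dose | Not in OLE | OLE entrant | Difference (weeks) |
|---|---|---|---|
| Day 85 | 112/7 = 16.0 | 112/7 = 16.0 | 0 |
| Day 57 (Week 12 missed) | 84/7 = 12.0 | 112/7 = 16.0 | 4.0 |
| Day 29 | 56/7 = 8.0 | 112/7 = 16.0 | 8.0 |
| Day 1 only | 28/7 = 4.0 | 112/7 = 16.0 | 12.0 |

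The Week 12 case is overstated by 4/12 = 33%.

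**Gaps between doses.** With doses on Days 1 and 85 only, the non-OLE rule gives (min(112, 113) - 1 + 1)/7 = 16.0 and the OLE rule gives 16.0. Neither subtracts an interior gap.

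**Over-study duration.** With OLE dosing through Day 337, the SAP formula gives (min(337 + 13, 365) - 1 + 1)/7 = 350/7 = 50.0 weeks for any number of double-blind doses. The OLE part is (350 - 113 + 1)/7 = 238/7 = 34.0. Adding the dose-capped double-blind part gives 16 + 34 = 50 with full dosing, 12 + 34 = 46 with Week 12 missed, and 4 + 34 = 38 with Day 1 only.

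**Corrected OLE branch.** [min(last dose + 27, OLE first dose - 1) - first dose + 1]/7 with OLE on Day 113 gives 4.0, 8.0, 12.0 and 16.0 for last doses on Days 1, 29, 57 and 85. These equal the non-OLE branch in each case.

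**Effect of visit windows.** With the last dose on Day 83 and OLE on Day 115, the SAP rule gives 114/7 = 16.29 and the corrected rule gives min(110, 114)/7 = 15.71. A fully dosed subject moves by 4/7 = 0.57 week.

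**Arm level, by assumption.** If 5% to 15% of an arm's OLE entrants miss the Week 12 dose, their mean duration is overstated by 0.05 × 4 = 0.2 to 0.15 × 4 = 0.6 weeks.

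**The case against.** The best defence is that the OLE rule matches the SAP's own safety period. SAP 3.3 runs the double-blind safety period from first dose to first OLE dose, and SAP 4.7.1 assigns adverse events on the same boundary. A dose-capped duration can be shorter than the window in which events are counted. That is true and is a real cost of changing the rule. It does not justify the present text, because the item is labelled treatment duration, and both the non-OLE rule and the OLE-period rule stop a fixed number of days after the last dose.

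Three further objections stand as limits.

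- Missed doses remain visible in the dose-count table and the listings. Compliance runs to the actual last administration, so for an OLE entrant it also spans missed double-blind doses unless it is split by period, which the SAP leaves optional. If it is split, one dose of one counts as full compliance.
- The Day 1 only case is extreme. It needs three consecutive missed doses and then OLE entry, and Protocol 4.9 lists severe noncompliance as grounds for withdrawal. A reader might infer that formally discontinued subjects also reach OLE dosing. The protocol says only that they continue visits without dosing and does not say whether OLE drug is open to them. The point needs only missed doses.
- The non-OLE rule follows the last dose date, not each dose given.

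A reader might also infer that safety at each dose is computed against this duration, especially as the safety endpoint is worded as an incidence rate. Protocol 8.7.1 presents numbers and percentages of subjects, and SAP 4.7.1 defines no person-time or exposure-adjusted rate.

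**Conclusion.** The inconsistency is real. For OLE entrants whose final double-blind dose or doses were missed, SAP 4.5 overstates treatment duration relative to its own non-OLE rule: by 4 weeks for a missed Week 12 dose, and by 12 weeks at the extreme. These figures assume nominal visit days and an OLE start on Day 113. The arm-level shift of 0.2 to 0.6 weeks rests on an assumed missed-dose rate. A difference in bias between arms is possible but cannot be shown from the documents.

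The consequence is limited to the descriptive double-blind and over-study duration summaries. No planned efficacy result or adverse event percentage changes. It is worth correcting because the remedy is cheap.

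**What to change.** In SAP 4.5, replace the double-blind formula for OLE entrants with:

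[min(DB last dose date + 27, OLE first dose date - 1) - DB first dose date + 1]/7

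Define over-study duration for OLE entrants as the double-blind duration plus the OLE duration. The two parts do not overlap, since the first ends no later than the day before the first OLE dose.

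Add a table footnote saying that gaps between doses are not subtracted in either branch, and that the duration may be shorter than the double-blind safety period in SAP 3.3. The disposition item in SAP 4.1 continues to report time in the period.

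The cost is a small SAP edit and minor programming, with no new data and no effect on subjects. The downsides are the shift of up to about 0.6 week for fully dosed subjects within the visit windows, and the mismatch with the safety window that the footnote discloses.

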4.6. Efficacy Analyses

All efficacy analyses will be performed in the mITT analysis set. Actual stratification factors based on EDC data will be used for efficacy analyses. The statistical analyses of the primary and key secondary endpoints will be repeated in PP analysis set. Analysis based on the mITT analysis set will be the primary analysis and the analyses based on other analysis sets will be considered as the supportive analyses.

Descriptive statistics will be provided for OLE data analyses in observed cases by all randomized subjects who enter OLE period as well as the DB treatment group, unless otherwise specified.

4.6.1. Multiplicity Adjustment

As this is a dose finding study, there is no multiplicity adjustment planned for the comparisons of multiple doses of KPL-716 versus placebo.

4.6.2. Analyses of Primary Efficacy Endpoint

The primary analysis for the efficacy endpoints will be based on the mITT analysis set.

The following null hypothesis (H0) and alternative hypothesis (H1) will be tested for each KPL-716 dose against placebo:

- H0: No treatment difference between KPL-716 and placebo.
- H1: There is a treatment difference between KPL-716 and placebo.

The primary estimand for the primary endpoint is defined in [Table 1](#), using the treatment policy/hypothetical strategies. Off-study treatment data up to Week 16 will be included in the analysis. Data will be set to missing values after prohibited/rescue medication that impact efficacy analyses prior to Week 16, and the subject's worst post baseline observation before the time of the medication usage will be carried forward (WOCF) to impute missing endpoint value (for subjects whose postbaseline values are all missing, the baseline will be used to impute).

Missing data at Week 16 will be imputed with Multiple Imputation (MI) method. This MI method will use subjects excluding those who used prohibited/rescue medications that impact efficacy analyses prior to Week 16 as input. See [Appendix 7.1](#) for the sample SAS code for the imputation.

Each of the imputed complete data will be analyzed by fitting an ANCOVA model with treatment and randomization stratification factors of sex and years since the first nodule observed (i.e., ≥ 10 vs. < 10 years) as fixed effect factors, baseline as covariate. The imputation number will be about 40. Statistical inference obtained from all imputed data will be combined using Rubin's rule. Descriptive statistics including number of subjects, mean, standard error, and least squares

(LS) mean percent changes (and standard error) will be provided. In addition, difference of each KPL 716 dose group against placebo in LS means and the corresponding 95% confidence intervals (CI) will be provided along with the p-values

Sensitivity analyses

The sensitivity analyses will be conducted for the same estimand for the primary endpoint. There are two sensitivity analyses planned for the primary efficacy endpoint to handle missing data at Week 16 after the WOCF method is applied for the subjects who use prohibited/rescue medications that impact efficacy.

- Sensitivity 1 (WOCF/LOCF): Missing data at Week 16 will be imputed with last observation carried forward (LOCF) method.
- Sensitivity 2 (WOCF/Observed): Missing data at Week 16 will not be imputed (observed) .

Same as the primary analysis, ANCOVA models will be used for the sensitivity analyses.

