1.5. Determination of Sample Size

The Phase 2b sample size calculation is based on the primary efficacy endpoint (percentage change from baseline of WI-NRS at Week 16) using a two-sample t-test.

Approximately 180 subjects in total will be equally randomized to the 4 arms of Phase 2b. At Week 16, 53% and 30% reduction in weekly average of WI-NRS are assumed for KPL-716 and placebo arms, respectively. For each comparison, assuming treatment effect of 23% difference in weekly average WI-NRS reduction from baseline at Week 16 and standard deviation of 35%, and two-sided alpha of 0.05, 38 subjects in each arm will provide 80% power to detect the treatment effect. Approximately 45 subjects in each arm will be randomized assuming 15% drop out during the 16 weeks of treatment.

The sample size calculation was performed using nQuery version 8.5.

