7. APPENDIX

7.1. Multiple Imputation Sample SAS Code

1. Data after use of rescue/prohibited medications will be set to missing and imputed with worst post baseline scores.
2. Impute intermediate missing data. 40 datasets with a monotone missing pattern will be obtained, induced by Markov Chain Monte Carlo (MCMC) method on subjects who have not taken the prohibited medications and/or rescue medications prior to Week 16. Variables in MCMC modeling includes actual stratification factors: sex, years since first PN diagnosis, treatment, baseline score, and percent change scores of weeks 1-16.

```
proc mi data=dataset seed=201 n impute=40 out=dat_mc;  
  mcmc impute=monotone;  
  var sex years since_first_diagnosis baseline treatment_group  
  percent_change_weeks 1-16;  
  run;
```

3. For each the imputed dataset with monotone missing pattern in Step 2, the remaining missing data will be imputed using the regression method for the monotone pattern with adjustment for covariates including sex, years since first PN diagnosis, treatment, baseline score, and scores of weeks 1-16 as covariates..

```
proc mi data=dat_mc n impute=1 seed=201 out=dat_mi;  
  by _imputation_;  
  class sex years since_first_diagnosis treatment_group;  
  monotone method=reg;  
  var sex years since_first_diagnosis baseline treatment_group  
  percent_change_week 1-16;  
  run;
```

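### The primary multiple imputation is fitted only on subjects without efficacy-impacting rescue or prohibited medication before Week 16, which discards valid pre-use scores and, if rescue follows current itch, makes imputed values for dropouts somewhat too favourable

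*SAP*

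**What the plan says.** The primary endpoint is percent change in weekly average WI-NRS at Week 16. SAP 4.6.2 treats two groups differently.

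- **Users of rescue or prohibited medication judged to affect efficacy, before Week 16.** Scores after use are set to missing and replaced by the worst earlier post-baseline value (WOCF). Table 1 labels this a hypothetical strategy.
- **Other subjects with missing Week 16 data.** Values come from multiple imputation (MI), for which 4.6.2 states: "This MI method will use subjects excluding those who used prohibited/rescue medications that impact efficacy analyses prior to Week 16 as input".

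Appendix 7.1 carries the same rule. Step 1 applies WOCF. Step 2 creates 40 monotone datasets, "induced by Markov Chain Monte Carlo (MCMC) method on subjects who have not taken the prohibited medications and/or rescue medications prior to Week 16". Step 3 builds on these: "For each the imputed dataset with monotone missing pattern in Step 2, the remaining missing data will be imputed using the regression method". Both imputation steps therefore run without the users. The SAP gives no reason.

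Protocol 6.1 allows rescue from 4 weeks after randomization, for a symptom exacerbation serious enough to need intervention. SAP 4.6.6 defines rescue for analysis as specified drug classes used against itch or PN lesions with a significant effect on efficacy interpretation, identified by blinded medical review.

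**The concern.** Two things look wrong.

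First, only scores after use are declared missing. The weeks before first use are genuine observations, but the restriction removes the whole subject and those weeks with them.

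Second, being free of impactful rescue up to Week 16 is a post-randomization status connected with itch. Regressions of later weeks on earlier weeks, fitted only in subjects who stayed well enough to avoid rescue, can predict too much improvement for someone who drops out.

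At stake are the arm LS means of the primary analysis and, through SAP 4.6.4, of the other continuous efficacy endpoints. If rescue differs by arm, the distortion does too, and this study is meant to separate doses.

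**Working it through.** **Design figures (SAP 1.5).** The plan states: "53% and 30% reduction in weekly average of WI-NRS are assumed for KPL-716 and placebo arms, respectively". It adds: "standard deviation of 35%, and two-sided alpha of 0.05, 38 subjects in each arm will provide 80% power to detect the treatment effect". It also states: "Approximately 45 subjects in each arm will be randomized assuming 15% drop out during the 16 weeks of treatment".

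- Normal approximation: n = 2 × (1.960 + 0.842)² × 35² / 23² = 36.4, so 37 per arm.
- Exact two-sample t-test power: 79.6% at 37 and 80.7% at 38, so 38 is reproduced.
- Dropout: 38 / 0.85 = 44.7, so 45 per arm and 180 in total.

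The sample size is not in dispute. It supplies the means, SD and dropout rate used below.

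**Simulation set-up.** One active arm and placebo, 60,000 subjects each. Weekly percent changes for Weeks 1 to 16 have Week 16 means of -53 and -30 and SD 35 before truncation to -100/+30. Overall dropout is 15%, depending on the previous week's itch. Imputation is sequential regression on baseline, treatment and earlier weeks; sex and disease duration were not simulated. The documents give no rescue rate, so placebo rescue was set at 10%, 20%, 30% and 40%. With rescue driven by current itch, active rescue followed at about 3%, 8%, 13% and 20%.

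**Mean Week 16 percent change for dropouts who receive MI, rescue driven by current itch:**

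| Placebo rescue | Placebo: true, no rescue | SAP rule | Pre-use weeks kept | Active: true, no rescue | SAP rule | Pre-use weeks kept |
|---|---|---|---|---|---|---|
| 10% | -22.4 | -24.0 | -22.4 | -42.8 | -43.1 | -42.0 |
| 20% | -24.2 | -26.9 | -24.4 | -43.8 | -45.5 | -43.1 |
| 30% | -25.8 | -30.3 | -25.6 | -44.7 | -47.2 | -44.4 |
| 40% | -27.3 | -34.1 | -27.2 | -45.8 | -49.1 | -45.4 |

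From unrounded values, the SAP rule is too favourable by 1.5, 2.8, 4.5 and 6.9 points on placebo and by 0.4, 1.7, 2.5 and 3.3 on active. Keeping pre-use weeks brings both arms within about 0.7 points of the no-rescue values. A second simulation, at 27% placebo and 13% active rescue, gave about 4 and 3 points, falling to about 1 when pre-use weeks were kept.

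**Effect on the treatment difference.** Shift = (active share imputed × active bias) − (placebo share imputed × placebo bias).

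- 10%: 0.124 × (-0.37) − 0.161 × (-1.52) = +0.20
- 20%: 0.119 × (-1.72) − 0.149 × (-2.76) = +0.21
- 30%: 0.114 × (-2.52) − 0.136 × (-4.48) = +0.32
- 40%: 0.109 × (-3.30) − 0.124 × (-6.85) = +0.49

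The assumed difference is -23, so a positive shift is toward zero. The standard error of the difference at 45 per arm is 35 × √(2/45) = 7.4. The largest shift, 0.49, is 0.07 of it. For scale, t-test power at 45 per arm is 86.9% for 23 points and 85.5% for 22.5.

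**Boundary case.** When rescue depended only on Week 4 itch, which the imputation model already contains, the bias against the no-rescue target was within 0.6 points in both arms at every rescue rate.

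**The case against.** **Size.** The strongest reply is that the primary comparison barely moves. The shift is a small fraction of one standard error and usually conservative, in a dose-finding study without multiplicity adjustment. That stands. A reader might infer that the drug effect is inflated or a dose decision endangered; the figures do not support this.

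**Mechanism.** A reader might infer that dropouts in every arm will certainly be scored too well. The documents give no rescue rate, correlation structure or dropout mechanism, and the boundary case shows almost no bias. The claim is conditional.

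**Scope.** The exclusion does not cover all rescue. Only use judged to affect efficacy, and only before Week 16, counts. A dropout with such use beforehand receives WOCF, not MI.

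**Rationale.** Because Step 1 fills in WOCF constants before Step 2, excluding users keeps those constants out of the imputation model. That purpose is defensible but does not require deleting genuine pre-use weeks.

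**Safeguards.** Sensitivity 1 (LOCF) and Sensitivity 2 (observed cases) both avoid the restricted imputation, and the key secondary responder endpoints use non-responder rules. Neither sensitivity analysis refits the model with users included, so neither isolates the effect.

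**Target.** Measured against the values dropouts would have had under the SAP's WOCF rule, the gap is larger: 3.7 to 15.8 points on placebo and 1.5 to 9.4 on active. It would be wrong to attribute all of this to the restriction. Keeping pre-use weeks still misses that target (-25.6 against -19.4 for placebo at 30% rescue), because the model then imputes as if no rescue occurred.

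**Other weeks.** Read literally, 4.6.4 leaves a later user's missing early week covered by neither MI nor WOCF. A reader might call this a definite gap. But the footnote to Table 1 gives other weeks a similar strategy, so the cut-off can be read as the analysed week. This is minor.

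**Conclusion.** The restriction is explicit, appears in both places, and is avoidable. It discards valid pre-use scores and selects the imputation sample on post-randomization itch. If rescue follows current itch, imputed values for dropouts are too favourable by an estimated 1.5 to 6.9 points on placebo and 0.4 to 3.3 on active, against a no-rescue target at assumed placebo rescue of 10% to 40%. If rescue depends only on itch already in the model, the bias is near zero. The treatment difference changes by under 1 of 23 points whichever target is used (at most 0.49 against no rescue, 0.93 against the WOCF rule). The direction is toward zero when placebo uses more rescue; other rescue or dropout patterns could reverse it. The rescue rates, correlation structure and dropout mechanism are assumptions. The point is worth correcting because the repair is cheap, not because the primary conclusion is at risk.

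**What to change.** In SAP 4.6.2 and Appendix 7.1:

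1. Keep all mITT subjects in the imputation input, with scores after first efficacy-impacting rescue or prohibited use set to missing.
2. Run Steps 2 and 3 on everyone.
3. Before the ANCOVA, overwrite users' post-use values with the planned WOCF value.
4. State that dropouts without such use are imputed to a no-rescue target.

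WOCF constants still stay out of the imputation model, and the WOCF rule for users is unchanged. Running the same steps for other weeks would also settle how a later user's missing early week is filled under 4.6.4. The cost is a few sentences of SAP text and a reordered program step. No new data are needed.
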